4.2 Secondary Outcome Measure

1. 6 month local control, defined as a 6-month rate of any new, recurrent or progressing (as defined by RANO criteria) tumor within the planning target volume compared to pre-SRS on any post-treatment MRI by 6 months. Follow-up MRIs will be fused with the planning scan for this assessment.
2. 6 month radiographic radiation necrosis, defined as brain imaging findings (MRI, MR Perfusion, MR Spectroscopy, and/or PET) consistent with radiation necrosis.
3. 12 month local control
4. 12 month symptomatic radiation necrosis
5. 12 month radiographic radiation necrosis
6. Evaluation of 12 month local control rate by SRS modality (Gamma Knife versus Linear Accelerator)
7. Evaluation of 12 month local control rate by single agent versus multi-agent ICI
8. Evaluation of 12 month local control rate by melanoma versus non-melanoma brain metastases
9. Evaluation of 12 month symptomatic radiation necrosis rate by SRS modality (Gamma Knife versus Linear Accelerator)
10. Evaluation of 12 month symptomatic radiation necrosis rate by single agent versus multi-agent ICI
11. Evaluation of 12 month symptomatic radiation necrosis rate by melanoma versus non-melanoma brain metastases

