A potential solution to this problem involves dose-reduced SRS to a level which substantially reduces radionecrosis risk without sacrificing the approximately 80-85% six-month local control provided by the present dosing schema, which from RTOG 90-05 has remained 24 Gy for lesions 0-2 cm, 18 Gy for lesions 2.1-3 cm, and 15 Gy for lesions 3-4 cm (Shaw et al., 2000). To maintain a dosing schema less toxic than the RTOG 90-05 regimen while remaining within SRS doses established by Level I evidence to provide local control (Brown et al., 2017), we propose the following dose-reduced SRS protocol for this *Radiosurgery Dose Reduction for Brain Metastases on Immunotherapy* (RADREMI) prospective pilot study: 18 Gy (0-2 cm lesions), 14 Gy (2.1-3 cm lesions), and 12 Gy (3-4 cm lesions) for brain metastases patients receiving at least one immunotherapy agent. These doses are consistent with Level I evidence comparing SRS with whole brain radiation therapy for metastatic brain disease, which revealed that SRS doses of 12-20 Gy were sufficient to provide local control (Brown et al., 2017). For perspective, it is important to remember that RTOG 90-05 was not a dose finding study, but rather a dose tolerance study; subsequent work has established improved local control compared to RTOG 90-05 while using lower doses than the RTOG 90-05 regimen (Shehata et al., 2004; Colaco et al., 2016). Given the efficacy of immunotherapy alone in treating melanoma brain metastases (Tawbi et al., 2018), it is reasonable to hypothesize that a lower SRS dose than the RTOG 90-05 schema will result in a combinatorial effect sufficient to provide local control without resulting in the 20% symptomatic necrosis rate seen with the present dosing schema (Martin et al., 2018).

Summary and Rationale

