In summary, this study seeks to assess the efficacy and safety of radiosurgery dose reduction for brain metastases patients receiving immunotherapy. We hypothesize that: 1. Dose-reduced SRS will reduce the risk of radionecrosis compared to the 16% average rate per patient from the existing concurrent SRS + ICI literature (Skrepnik et al., 2017; Martin et al., 2018) with current SRS dose, and 2. Dose-reduced SRS demonstrates non-inferior efficacy (measured primarily through six-month local tumor control) compared to the 80% local control rate associated with the RTOG 90-05-established SRS dosing parameters. For the purposes of this study, radionecrosis will be defined as clinical symptomatology following SRS requiring steroid utilization and/or operative intervention in combination with imaging features strongly suggesting radionecrosis as demonstrated utilizing routine MRI, MR Perfusion, MR Spectroscopy, and/or PET imaging. Although the definition of concurrent SRS+ICI has varied greatly in the literature, ranging from 2 weeks to 4 months with some studies defining administration within 4 months as concurrent (Anderson et al., 2017; Chen et al., 2018); for the purposes of this study, concurrent therapy will be defined as ICI administered within 30 days of SRS. We also hope to explore SRS radionecrosis rates in multi-agent versus single-agent immunotherapy, as well as in melanoma versus non-melanoma brain metastases. Local control will be defined as a less than 20% increase in tumor size following SRS, as previously described using Response Assessment in Neuro-Oncology (RANO) criteria (Lin et al., 2015).

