14.4 Sample Size

An optimum one-stage design is planned. We specify a historical 6 month symptomatic radiation necrosis rate of 16% and an expected 6 month symptomatic radiation necrosis rate of 5%. Then, to achieve a power of 80% and control the type I error below 10%, a total of 40 patients evaluable for symptomatic radiation necrosis will be enrolled in the study. If at most 4 patients will experience symptomatic radiation necrosis in 6 months, the proposed dose reduction is claimed to be desirable. Otherwise, it is undesirable. We assume that at most 5% of the patients will not be evaluable for symptomatic radiation necrosis, which results in a total sample size of 42. In addition, we will add an interim analysis for the 6 month local control rate. When 20 patients have been enrolled in the study with their local control outcome being available, we will conduct a binomial exact test for the null hypothesis that the proposed method can maintain a 6 month local control rate of at least 75%. If p-value of this binomial test is less than 0.05, we will reject the null hypothesis and terminate this study earlier for futility.

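### Section 4.2 defines 6-month local control as the rate of local failure, the opposite of what Section 2 and the interim test in 14.4 mean by the term

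*Combined protocol and SAP*

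**What the plan says.** Four parts of the combined protocol and SAP bear on this.

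- **Section 4.2, item 1 (outcome definition).** The item opens: "6 month local control, defined as a 6-month rate of any new, recurrent or progressing". The quantity in full is a "6-month rate of any new, recurrent or progressing (as defined by RANO criteria) tumor within the planning target volume", judged against the pre-SRS state on any post-treatment MRI up to 6 months. Items 3 and 6 to 8 (12-month local control, overall and by SRS modality, ICI regimen and histology) give no definition of their own.
- **Section 2 (Summary and Rationale).** "Local control will be defined as a less than 20% increase in tumor size following SRS". The efficacy hypothesis is non-inferiority "compared to the 80% local control rate associated with the RTOG 90-05-established SRS dosing parameters". The same section speaks of the "approximately 80-85% six-month local control provided by the present dosing schema" and cites 87 to 91% for single-fraction SRS.
- **Section 14.4 (interim analysis).** "When 20 patients have been enrolled in the study with their local control outcome being available", an exact binomial test is made of "the null hypothesis that the proposed method can maintain a 6 month local control rate of at least 75" percent. The consequence is: "If p-value of this binomial test is less than 0.05, we will reject the null hypothesis and terminate this study earlier for futility". The section does not say which definition of local control supplies the count, or whether the test is one-sided.
- **Section 14.8.** Local control at 6 and 12 months is to be estimated by Kaplan-Meier. The event is not named.

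**The concern.** The formal outcome definition is the complement of the quantity it names. In Section 2 and in 14.4 a high value is good. Under 4.2 a high value means that most patients have tumor in the treated volume. This is separate from which growth criterion applies: whichever is chosen, 4.2 points the wrong way.

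The location matters. Section 4.2 is the outcome-measure section and the only place that gives local control a time window and a target volume. The 12-month items depend on it. The same term is also the variable in the trial's one pre-specified statistical stopping rule. Someone who builds a case report form, a derived variable or a results table from 4.2 would enter failures under the name of control.

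**Working it through.** **Step 1. Direction of each statement.**

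| Place | What is counted | High value means |
|---|---|---|
| 4.2, item 1 | new, recurrent or progressing tumor in the target volume | poor outcome |
| Section 2, definition | growth below 20% | good outcome |
| Section 2, benchmarks | 80%, 80 to 85%, 87 to 91% control | good outcome |
| 14.4, interim null | control of at least 75% | good outcome |

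Only 4.2 is reversed. Its sentence is complete and grammatical, so a PDF reading fault does not explain it.

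**Step 2. Interim limit.** The plan states no stopping limit and no operating characteristics for this test, so there is no figure of its own to reproduce. Inputs from 14.4: n = 20, null rate 0.75, stop if p is below 0.05. Assumption: a one-sided lower-tail test, inferred from the form of the null.

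The p-value for x patients is P(X ≤ x), with X ~ Binomial(20, 0.75).

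- x = 11: p = 0.0409, stop.
- x = 12: p = 0.1018, continue.

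The rule is therefore to stop at 11 or fewer of 20.

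**Step 3. Probability of stopping under each reading.** Let c be the true 6-month control rate. With the direction corrected, X ~ Binomial(20, c). With 4.2 taken literally, X counts failures, so X ~ Binomial(20, 1 − c). In both cases P(stop) = P(X ≤ 11).

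| True control c | Failure 1 − c | P(stop), direction corrected | P(stop), 4.2 taken literally |
|---|---|---|---|
| 0.75 | 0.25 | 0.041 | 0.9991 |
| 0.80 | 0.20 | 0.010 | 0.9999 |
| 0.85 | 0.15 | 0.0013 | above 0.9999 |
| 0.87 | 0.13 | 0.0005 | above 0.9999 |
| 0.91 | 0.09 | below 0.0001 | above 0.9999 |
| 0.20 | 0.80 | 0.9999 | 0.010 |

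The last row shows the reverse error: if only 20% of patients had control, the literal reading would almost never stop the trial.

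**Step 4. One worked case.** Suppose 16 of 20 patients have control. Read as control, p = P(X ≤ 16) = 0.77 and the trial continues. Read as 4.2 events, the count is 20 − 16 = 4, p = P(X ≤ 4) = 3.9 × 10⁻⁷, and the trial stops.

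**Step 5. Sensitivity to sidedness.** A two-sided exact test gives p = 0.065 at 11 of 20 and p = 0.017 at 10 of 20, so the lower limit becomes 10. P(X ≤ 10) is then 0.996 at a rate of 0.25 and 0.9994 at 0.20. The contrast between the two readings is unchanged.

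**The case against.** The strongest reply is that nobody would run the test the wrong way round. The null in 14.4 speaks of maintaining a rate of at least 75%, and rejecting it means futility; that makes sense only if high is good. Every benchmark in Section 2 has the same direction. Section 14.4 does not cite 4.2, Section 2 supplies a definition with the right direction, and Section 8.6 sends the assessment to RANO-BM, where progression is the adverse event. Item 1 still identifies the event, the place and the window correctly, so image reads and event dates would not change; control is simply the complement. The phrasing follows the pattern of the necrosis definition in 4.1, which suggests a slip of wording.

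Most of this stands. A reader might infer from 4.2 and 14.4 together that the plan would terminate a trial with good local control. The documents do not support that: the link from 4.2 to the interim test is not stated, and the wording of the test shows the intended direction. The near-certain stopping probabilities describe a literal misuse, not the planned rule. It would also be too strong to call this the only way the trial can stop early, because Section 17 lets the investigators or the DSMC close it.

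The reply does not remove the error. The Section 2 definition cannot simply take the place of 4.2, because it has no time window, no target volume and no rule for new or recurrent tumor. Nothing in Section 14 says explicitly which way to read 4.2.

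**Conclusion.** The definition in 4.2, item 1 is wrong as written: it names the local failure rate local control and conflicts with Section 2 and 14.4. It should be corrected, but it does not undermine the design. The intended direction is clear enough that wrongful termination is unlikely. The realistic harm is mislabeled data or results for local control at 6 months and, through the items that depend on item 1, at 12 months.

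The computed contrast at the interim look (0.9991 against 0.041 at 75% true control, 0.9999 against 0.010 at 80%) rests on three assumptions: a one-sided exact test, 20 evaluable patients, and literal use of 4.2 in the count. The third is hypothetical. The inversion itself is plain from the text and needs no assumption.

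**What to change.** 1. In 4.2, item 1, define 6-month local control as the proportion of patients in whom no post-treatment MRI up to 6 months shows new, recurrent or RANO-progressing tumor inside the planning target volume.
2. Reconcile Section 2 with it, so that one definition covers growth and also new or recurrent tumor.
3. Have items 3 and 6 to 8 of 4.2, and the interim test in 14.4, refer to item 1. State in 14.4 that the count is of patients with control and that the test is one-sided in the lower tail, if that is the intention.
4. In 14.8, state that the Kaplan-Meier event is local failure and that local control is the event-free proportion.

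The cost is a few sentences. No change follows for treatment, visits, imaging, sample size or the 75% threshold.

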5. ELIGIBILITY CRITERIA

5.1 Inclusion Criteria

1. Brain MRI-confirmed 1-10 solid tumor brain metastases (Yamamoto et al., 2014)
2. Biopsy-confirmed primary malignancy
3. ds-GPA estimated median survival of at least 6 months, for histologies not included in the ds-GPA, publications or noted online at brainmetgpa.com, the PI will use either published or validated data or their best clinical judgment to determine the patient's expected survival
4. Stereotactic radiosurgery candidate per treating Radiation Oncologist
5. ≥ 18 years old at the time of informed consent
6. Ability to provide written informed consent and HIPAA authorization
7. ALC $> 800/\text{ul}$ (Ku et al., 2010)
8. Patients currently on cytotoxic chemotherapy are eligible
9. Patients receiving ICI up to 30 days prior to delivery of SRS are eligible

10. Patients having undergone operative resection for metastatic brain disease within 30 days of immune checkpoint inhibitor (ICI) administration are eligible.

5.2 Exclusion Criteria

1. Major medical illnesses or psychiatric impairments, which in the investigator's opinion will prevent administration or completion of the protocol therapy and/or interfere with follow-up
2. Patients unable to receive MRI Brain
3. Patients with more than 10 brain metastases on MRI Brain
4. Any lesion > 4 cm maximum diameter
5. Total volume of metastatic disease more than 30 cm³
6. Previous whole brain radiation therapy
7. For Cohort 1: Previous stereotactic radiosurgery where the 50% isodose line overlaps with current treatment field
8. For Cohort 2: Patients whose treatment will have a dose overlap within the target from prior treatments of 20% or greater
9. Already receiving chronic dexamethasone (chronic = \geq 2 weeks) prior to SRS
10. Not a radiosurgical candidate per Radiation Oncology discretion
11. Existing autoimmune disease
12. Patients who have an unknown primary
13. Histology not amenable for SRS (i.e. lymphoma). (Small Cell Lung Cancer IS amenable.)

6. STUDY DESIGN

This is a prospective multi-site, single arm, pilot study to determine the symptomatic radiation necrosis rate at 6 months utilizing dose-reduced stereotactic radiosurgery with immunotherapy for subjects with a diagnosis of 1-10 brain metastases from MRI and tissue diagnosis of primary malignancy.

7. PATIENT REGISTRATION

Potential patients will be identified and recruited per the recommendation of medical oncologists, tumor boards, Department of Radiation Oncology, outside physicians, or self-referral. No advertisement will be used to recruit subjects. Patients who appear to be eligible for this trial will undergo the Informed Consent Process and be screened for eligibility utilizing the eligibility criteria. Eligible patients who complete the Informed Consent Process will be registered in the OnCore® database and assigned a patient ID number. Regulatory files will be maintained by the Radiation Oncology Research Office. Applicable regulatory documents must be completed and on file prior to registration of any patients.

8. STUDY PROCEDURES

8.1 Cohorts Description

This study will be divided into 2 main cohorts as described below. Both cohorts will have the same procedures completed and will follow the same timelines up to the 6-month follow-up. After 6 months, subjects will be followed on the most recent calendar for up to 5 years post last SRS.

Cohort 1: All subjects initially screened and treated for this study.

Cohort 2: If a subject is treated and during follow-up scans new lesion(s) are found, they may be treated for those new lesion(s). These must be patients who have not had a negative outcome or end-point event while enrolled on Cohort 1. These subjects will be consented on a cohort specific consent and follow all procedures listed below.

Subjects may be treated multiple times, per procedures below.

8.2 Baseline/Screening Procedures

The following will be completed prior to radiosurgery:

1. Written informed consent and HIPAA authorization
2. Diagnostic MRI Brain
3. Medical history and clinical examination performed by physician from neurology, neurosurgery, medical oncology, or radiation oncology.
4. Absolute Lymphocyte Count (ALC) – total number of immune cells in mL of blood
5. Baseline ds-GPA, and KPS; for histologies not included in the ds-GPA, publications or noted online at brainmetgpa.com, the PI will use either published or validated data or their best clinical judgment to determine the patient's expected survival

8.3 Stereotactic Radiosurgery

Stereotactic radiosurgery will be delivered on all patients utilizing gamma knife or linear accelerator based techniques as per RADREMI dosing criteria (Section 10 Table 1) based on tumor diameter. All apparent, previously untreated brain metastases will be treated with radiosurgery at this time.

If any of the following occurs during the MRI Brain planning scan, the subject will be withdrawn from study, not treated on protocol, and replaced:

- The total number of brain metastases sums greater than 10. The subject will be withdrawn and not treated on protocol.
- The total volume of brain metastases is greater than 30 cm³. The subject will be withdrawn and not treated on protocol.

8.4 Follow-Up

Following delivery of stereotactic radiosurgery, all patients will be monitored clinically and with serial MRI Brain scans to determine local control and rate of radiation necrosis. Additional imaging and testing may be performed as deemed necessary by the treating physician.

Initiation/continuation of immunotherapy, chemotherapy and/or other systemic agents will be per medical oncologist discretion.

8.5 One Month Follow-Up

A detailed medical history, toxicity assessment and physical examination including vital signs along with a brain MRI will be performed at 4 weeks after radiosurgery.

8.6 Long Term Follow up

Subjects will be followed approximately every 3 months (+/- 30 days) after SRS for 1 year. A detailed medical history (including necessity of any steroid administration), toxicity assessment and physical examination including vital signs will be performed at each visit. Each follow-up over this time period will also include a Brain MRI with the following sequences: without contrast, with contrast, FLAIR, Diffusion Tensor Imaging (DTI) and Perfusion Weighted Imaging (PWI). The MRI will be analyzed per RANO BM criteria (Section 11) for assessment of local control. The MRI will also be analyzed for radiation necrosis as discussed in Section 12. Neurologic status will be assessed using the Neurologic Assessment in Neuro-Oncology (NANO) scale (Nayak et al., 2017).

After the 1-year (12-month) follow-up period, subjects will be followed according to their treating physician per standard of care every 3-6 months. MRI Brain obtained during this time period may be used for assessment of primary and secondary endpoints; however, are not mandated to be obtained at particular time intervals. Patients who are unable to travel to Indiana University for follow-up appointments will have records sent to Indiana University at each follow-up.

From year 2-5, the follow up period will be determined by their treating physician per standard of care, generally every 3-6 months. MRIs will be obtained per treating physician discretion.

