Only patients with measurable CNS disease at baseline should be included in protocols where objective CNS tumor response is the primary endpoint. For studies in which objective response is not the primary endpoint, the protocol must specify prospectively whether entry is restricted to those with measurable disease or if patients with non-measurable disease are also eligible.

- a. Assignment of CNS response is independent of systemic disease response. CNS lesions are to be assessed according to RANO-BM criteria, whereas non-CNS lesions would most typically be assessed according to RECIST 1.1 criteria.
- b. Generally, CNS lesions should initially be re-assessed by MRI at protocol-specified intervals 6–12 weeks apart, although there might be specific circumstances in which longer (or shorter) intervals are desirable. For patients who remain stable for extended periods of time, a longer interval between scans might be appropriate. All baseline assessments should be done as close as possible to the treatment start and no more than 4 weeks before the beginning of treatment.
- c. For previously treated lesions, we recommend documentation of how each lesion was previously treated (e.g., stereotactic radiosurgery, whole brain radiotherapy, surgical resection).
- d. When more than one measurable lesion in the CNS is present at baseline, all lesions up to a maximum of five CNS lesions should be identified as target lesions and will be recorded and measured at baseline. All measurements should be recorded in metric notation. Target lesions should be selected on the basis of

their size (longest diameter) and as those that can be measured reproducibly. For patients with recurrent disease who have multiple lesions, of which only one or two are increasing in size, the enlarging lesions should be prioritized as target lesions for the response assessment.

- e. Lesions with prior local treatment (i.e., stereotactic radiosurgery or surgical resection) can be considered measurable if progression has occurred since the time of local treatment. However, careful consideration should be given to lesions previously treated with stereotactic radiosurgery, in view of the possibility of treatment effect, which is discussed below. Whether such lesions can be considered measurable should be specified prospectively in the clinical protocol. If lesions not previously treated with local therapies are present, these are preferred for selection as target lesions.

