- f. A sum of the diameters for all target lesions will be calculated and reported as the baseline sum of longest diameters. All other CNS lesions should be identified as non-target lesions and should also be recorded at baseline. Measurements are not required and these lesions should be classified as present, absent, or unequivocal progression, and followed up.

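### Up to ten lesions are irradiated, but the assigned local-control method measures at most five, on a summed diameter, so treated lesions are not all judged by one test and failures may be missed

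*Combined protocol and SAP*

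**What the plan says.** Section 5.1 admits patients with "Brain MRI-confirmed 1-10 solid tumor brain metastases". Section 8.3 adds: "All apparent, previously untreated brain metastases will be treated with radiosurgery at this time". One patient can therefore have ten irradiated targets.

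Local control is described in three places:

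- Section 2 (Summary and Rationale) defines it as growth of less than 20% in tumor size after radiosurgery.
- Section 4.2, item 1, describes failure as new, recurrent or progressing tumor inside the planning target volume, compared with the pre-treatment state, on follow-up MRI fused with the planning scan. It refers the meaning of progression to RANO.
- Section 8.6 gives the reading method: "The MRI will be analyzed per RANO BM criteria (Section 11) for assessment of local control".

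The RANO-BM text in Section 11.1 (item 4d) says "all lesions up to a maximum of five CNS lesions should be identified as target lesions". They are chosen by size and by how reproducibly they can be measured. For all other lesions, item 4f says "Measurements are not required and these lesions should be classified as present, absent, or unequivocal progression, and followed up". Table 3 calls target progression when the sum of longest diameters rises at least 20% above its smallest value on study and at least one lesion grows by 5 mm or more. Unequivocal progression of a non-target lesion is also progressive disease. No sentence adapts the five-lesion limit or the sum to irradiated lesions.

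**The concern.** A five-target cap and a summed diameter suit a summary of response across the brain. The local-control outcome here asks a narrower question: whether each irradiated target stayed controlled. Under the assigned method, a treated lesion ranked sixth or lower needs no follow-up diameter and is read qualitatively, while the first five are read through a sum. Neither reading is the per-lesion growth rule that Section 2 suggests.

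Local control is a secondary outcome, but it carries the second study hypothesis (Section 2) and is the only endpoint in the interim futility test (Section 14.4). Missed failures would make an early stop less likely. Patients with many lesions would be most affected, so the planned comparisons by modality, drug regimen and histology could be distorted if lesion counts differ between those groups.

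**Working it through.** The plan gives no figure of its own on this point, so there is none to reproduce.

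**1. Share of treated lesions with no required diameter.** Inputs: up to 10 lesions (Sections 5.1 and 8.3) and at most 5 targets (Section 11.1). For m treated lesions the share is max(0, m − 5)/m.

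| Treated lesions | Unmeasured | Share |
|---|---|---|
| 1–5 | 0 | 0% |
| 6 | 1 | 17% |
| 7 | 2 | 29% |
| 8 | 3 | 38% |
| 9 | 4 | 44% |
| 10 | 5 | 50% |

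**2. The sum rule in the measured lesions.** Take five 20 mm lesions. Their volume is 5 × (π/6) × 2³ = 20.9 cm³, inside the 30 cm³ limit of Section 5.2. The baseline sum is 100 mm. One lesion grows to 30 mm and the others do not change. That lesion has grown 50% and meets the 5 mm condition, but the sum rises only 10/100 = 10%, so Table 3 does not call target progression. Section 2, read per lesion, would call it a failure. This can arise in patients with two to five lesions as well.

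**3. Illustrative size of the cap effect.** Assumptions, none of them in the documents: per-lesion six-month failure risk q = 5%; every failure among the five targets is found; no failure among the others is called unequivocal.

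With independent lesions, the probability that k lesions all stay controlled is 0.95^k:

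- k = 5: 0.774
- k = 6: 0.735, a gap from k = 5 of 3.9 points
- k = 8: 0.663, a gap of 11.0 points
- k = 10: 0.599, a gap of 17.5 points

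If half of the non-target failures are recognised, the gap is 0.95^5 × 0.975^(k−5) − 0.95^k, which gives 1.9, 5.4 and 8.3 points. If all are recognised, it is 0.

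With within-patient correlation ρ = 0.3 (beta-binomial, a = q(1−ρ)/ρ = 0.117, b = (1−q)(1−ρ)/ρ = 2.217, none recognised), the probabilities for k = 5, 6, 8 and 10 are 0.857, 0.843, 0.821 and 0.803. The gaps are 1.4, 3.6 and 5.3 points.

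Trial-wide, assume that 10%, 20% or 30% of patients have about 8 lesions and the rest five or fewer:

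- Independent, none recognised: share × 11.0 = 1.1, 2.2, 3.3 points
- Independent, half recognised: share × 5.4 = 0.5, 1.1, 1.6 points
- ρ = 0.3, none recognised: share × 3.58 = 0.4, 0.7, 1.1 points
- All recognised: 0

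**4. The interim test.** With 20 patients and a null of at least 75%, P(X ≤ 11) = 0.041 and P(X ≤ 12) = 0.102, so the trial stops at 11 or fewer controlled. If true control were 60%, the chance of stopping is 40.4%. If recorded control were 1 point too high (61%), it is 36.9%; if 3 points too high (63%), 30.0%.

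**The case against.** A reader might infer that local control is overstated in favour of the reduced dose. The documents do not support that as a finding, for four reasons.

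First, non-target lesions are still followed, and unequivocal progression of one counts as progressive disease (Table 3). Not requiring a measurement does not forbid one.

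Second, the qualitative test is not clearly the harder one to meet. With five 15 mm targets (sum 75 mm), one lesion alone must grow by 15 mm to lift the sum by 20%. A non-target lesion growing from 6 mm to 10 mm could be called unequivocal on sight, yet by itself it would fail the 5 mm condition if it were a target. The sum is also referred to its smallest value, whereas Section 4.2 compares with the pre-treatment state, so regrowth after shrinkage can count under one and not the other.

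Third, the Section 4.2 definition covers tumor in the planning target volume with no cap of its own, and Section 11.3 with Table 5 separates local from distant disease.

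Fourth, the illustration mixes two readings: complete per-lesion detection in targets, none in the rest.

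These arguments defeat a claim about direction or a firm size. They do not remove the mismatch. Section 4.2 sends progression back to RANO, Table 5 does not lift the cap, and nothing requires every irradiated lesion to be measured or scored alone.

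A reader might also infer that the unmeasured lesions fail more often because selection by size leaves out the smaller ones. The documents give no failure rate by lesion size.

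**Conclusion.** The point holds as a mismatch between the endpoint and its assigned reading method. For patients with 6 to 10 treated lesions, 17% to 50% of those lesions need no follow-up diameter; one half is the maximum and applies only at exactly ten. For patients with two or more lesions, the sum rule can hide growth of one. Failures may be missed or judged inconsistently.

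The net error cannot be fixed in size or direction, because the documents give neither the distribution of lesion counts nor the sensitivity of the qualitative reading. Under the assumptions stated in the working, the cap alone shifts trial-wide local control by 0 to about 3 points, and by at most about 0.4 to 1.1 points with correlation 0.3. It has no effect at five or fewer lesions. The sum rule is a separate source and is not in those figures. The success rule on symptomatic necrosis does not depend on this point. The matter is worth correcting because local control drives the interim look and the correction is cheap.

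**What to change.** In Sections 4.2, 8.6 and 11.1, state that for local control the five-target cap and the sum-of-diameters rule do not apply. Every irradiated lesion is measured on the planning scan and on each protocol MRI, and is scored individually by one progression criterion. Patient-level failure is failure of any irradiated lesion. Bring the Section 2 definition into line. The criterion should name its reference scan and say whether a minimum absolute increase applies, since 20% of a 3 mm lesion (the smallest measurable size in Section 11.1) is only 0.6 mm. As a check, repeat the local-control estimate in patients with five or fewer treated lesions.

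The cost is wording in these sections and up to five extra diameters per scan in patients with 6 to 10 lesions. Planning diameters already exist because they set the dose tier, and follow-up MRIs are already acquired and fused. The downside is some reading time and possibly a slightly lower reported local-control rate. The change is best made before images are read, because unrecorded diameters would otherwise need a second reading.
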